7.1.1.4.2 Concomitant Medications

The investigator or qualified designee will record medication, if any, taken by the subject during the trial treatment and during the Follow-Up Phase. All medications related to reportable SAEs should be recorded as defined in Section 7.2.

7.1.1.5 Disease Details and Treatments

7.1.1.5.1 Disease Details

The investigator or qualified designee will obtain prior and current details regarding disease status, including current stage, stage at diagnosis, diagnostic test(s).

7.1.1.5.2 Prior Treatment Details

The investigator or qualified designee will review all prior cancer treatments including surgery, ablative treatments, arterial therapies (such as radioembolization), radiation, and systemic treatments.

7.1.1.5.3 Liver Disease Details

The investigator or qualified designee will review liver disease history including risk factors for biliary cancer (such as prior or intercurrent liver infections including viral hepatitis, alcohol use, non-alcoholic steatohepatitis or fatty liver disease diagnosis or risk factors, cirrhosis/fibrosis, autoimmune disease, any other prior injury to biliary tract). Biliary obstruction history and drainage procedures (e.g., percutaneous drain or indwelling stent placement) at baseline, during

treatment, and during the Follow-Up Phase will be documented. History of and any new episodes of cholangitis will be documented at baseline, during treatment, and during the Follow-Up Phase.

7.1.1.5.4 Subsequent Anti-Cancer Therapy Status

The investigator or qualified designee will review all new anti-neoplastic therapy initiated after the last dose of trial treatment. If a subject initiates a new anti-cancer therapy within 30 days after the last dose of trial treatment, the 30 day Safety Follow-Up visit must occur before the first dose of the new therapy. Once new anti-cancer therapy has been initiated or if transition to palliative/end of life care such as Hospice enrollment occurs, the subject will move into Survival Follow-Up Phase.

7.1.1.6 Registration

All patients who consent will be registered in OnCore®, the UCSF Helen Diller Family Comprehensive Cancer Center Clinical Trial Management System (CTMS).

7.1.1.7 Enrollment

Once screening is completed, eligibility documents and checklist for all patients will be submitted via HIPAA-compliant method (e.g., secure e-mail or fax) for central review at UCSF by the Study Chair or designee. Once eligibility is confirmed by the Study Chair or designee, a study ID number will be assigned by the study coordinator and provided to treating investigator as confirmation of enrollment to proceed with protocol therapy.

7.1.1.8 Trial Compliance (Medication/Diet/Activity/Other)

See Section 5.2.3.3 and Appendix 11.2 for information on GM-CSF Patient Diary/Injection Record.

7.1.2 Clinical Procedures/Assessments

7.1.2.1 Adverse Event (AE) Monitoring

The investigator or qualified designee will assess each subject to evaluate for potential new or worsening AEs as specified in the Trial Flow Chart and more frequently if clinically indicated. Adverse experiences will be graded and recorded throughout the study and during the Follow-Up Phase according to NCI CTCAE Version 4.0 (see Appendix 11.3). Toxicities will be characterized in terms regarding seriousness, causality, toxicity grading, and action taken with regard to trial treatment.

All AEs of unknown etiology associated with pembrolizumab exposure should be evaluated to determine if it is possibly an immune-related adverse event (irAE). Please refer to section 7.2 for detailed information regarding the assessment and recording of AEs and irAEs.

7.1.2.2 Complete Physical Examination

The investigator or qualified designee will perform a complete physical examination according to institutional practice for the management and monitoring of patients with biliary cancers during

the screening period, at all follow up visits, and at end of treatment visit according to standard of care. Clinically significant abnormal findings during Screening should be recorded as medical history.

7.1.2.3 Vital Signs

The investigator or qualified designee will obtain vital signs at the timepoints specified in the Study Flow Chart (Section 6.0). Vital signs should include temperature, pulse, respiratory rate, oxygen saturation (pulse oximetry), weight and blood pressure. Height will be measured at screening only.

7.1.2.4 Eastern Cooperative Oncology Group (ECOG) Performance Scale

The investigator or qualified designee will assess ECOG status (see Appendix 11.4) at the timepoints specified in the Trial Flow Chart (Section 6.0).

7.1.2.5 Liver Function Assessment

The investigator or qualified designee will assess liver function by Child Pugh score (see Appendix 11.5) at the timepoints specified in the Study Flow Chart (Section 6.0).

7.1.2.6 Tumor Imaging and Assessment of Disease

Cross-sectional imaging with CT (preferred) or MRI abdomen plus pelvis and CT chest with/without or without contrast is required at screening, every 8 weeks (± 7 days) during first 6 months of treatment until ascertainment of PFS6, then every 8 weeks (± 14 days for patient convenience in scheduling on same day as infusions) until end of treatment. In subjects without evidence progression at treatment discontinuation, scans should be every 8 weeks ± 28 days for up to 1 year during Follow-Up Phase, then every 12 weeks ± 28 days (or more often if clinically indicated). for RECIST 1.1 response assessment¹ (see Section 6.0 – Study Flow Charts for timepoints). Multiphase/triphasic liver imaging should be included as appropriate. Additional baseline imaging such as PET scan, bone scan, or MRI brain are only required if clinically indicated by symptoms and/or to assess known bone metastases or other sites of known metastatic disease. All baseline evaluations will be performed as close as possible to the beginning of treatment and \leq approximately 28 days before C1D1. The same imaging modality/modalities should be used if possible throughout study unless there is a clinical indication to use a different modality (i.e. based upon Radiology recommendation to better assess a target lesion, an event of new contrast allergy, etc.). RECIST 1.1 measurements will be performed by a radiologist or qualified investigator.

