medical encounter, if travel to UCSF would confer hardship due to distance and/or due to initiation of new therapy. Subjects with at least possibly treatment-related AE of Grade > 1 will be followed until the resolution of the AE to Grade 0-1, assessment as chronic or irreversible by investigator, or until the beginning of a new anti-neoplastic therapy, whichever occurs first. Subjects who discontinue trial treatment for a reason other than disease progression will move into the Follow-Up Phase and should be assessed approximately every 8 weeks (56 ± 28 days) by radiographic imaging to monitor disease status. After 1 year, the Follow Up visits and imaging timepoints will occur approximately every 12 weeks (± 28 days). After 2 years, patients will be followed according to Survival Follow-Up phase.															
c	GM-CSF Patient Diary/Injection Record and instructions will be provided to each patient on Day 1 of Cycles 2 and 3 and any subsequent re-induction cycles. The completed diaries will be collected on Day 1 of Cycles 3 and 4 and after any re-induction cycles. See Appendix 11.2.														
d	Subjects with at least possibly treatment-related AE of Grade > 1 will be followed until the resolution of the AE to baseline or Grade 0-1, assessment as chronic or irreversible by investigator, or until the beginning of a new anti-neoplastic therapy, whichever occurs first. SAEs that occur within 90 days of the end of treatment or before initiation of a new anti-cancer treatment, whichever occurs first, will also be followed and recorded.														
e	Perform on women of childbearing potential only at screening and prior to each pembrolizumab infusion. If urine pregnancy results cannot be confirmed as negative, a serum pregnancy test will be required.														
f	See Section 7.1.3 and Table 5 for specific laboratory tests required as part of comprehensive metabolic panel.														
g	Or more often if clinically indicated.														

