7.1.6.4 Follow-Up Phase

Subjects who discontinue trial treatment for a reason other than disease progression will move into the Follow-Up Phase and should be assessed every 8 weeks (± 28 days) by radiography to monitor disease status. After 1 year, the imaging time point will occur every 12 weeks (± 28 days) or more often if clinically indicated. After 2 years in Follow-Up Phase, patients will discontinue active follow up and be followed only for survival according to Survival Follow-Up Phase (Section 7.1.6.4.2). Every effort should be made to collect information regarding disease status until the start of new anti-neoplastic therapy, disease progression, death, end of the study or if the subject begins retreatment with Second Course pembrolizumab as detailed in Section 7.1.5.2. Information regarding post-study anti-neoplastic treatment will be collected if new treatment is initiated.

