8.3.2 Secondary Endpoints

- 1) **Safety** endpoint assessment is described in Section 7.2. The safety endpoints are AEs graded using CTCAE (Version 4.0) criteria. Safety will be assessed by quantifying the toxicities and grades experienced by subjects who have received pembrolizumab plus GM-CSF induction, including SAEs and ECIs. Other safety endpoints include laboratory safety assessments, ECOG performance status, Child Pugh score, vital signs, and physical examinations. The incidence and frequency of dose reduction, treatment delays, and discontinuation for lack of tolerability will be quantified. Re-induction and Second Course safety events will be addressed in the same manner.

- 2) **Tumor PD-L1 status** will be measured by IHC and classified as positive or negative by central laboratory testing (QualTek Laboratories) using pre-specified cut-points.
- 3) A key secondary endpoint is %PFS6 (formerly primary endpoint, changed by amendment with addition of Expansion Cohort). For each patient, PFS will be calculated in days and months from date of first dose of protocol therapy to date of first documented radiographic and/or clinical disease progression or death from any cause. For patients removed from study for other reasons than progression or death, PFS will be censored at the date last known to be progression-free. See Section 5.9 for Replacement policy for non-evaluable patients. The %PFS6 will be calculated as the proportion of evaluable patients progression-free at 6 months. Censored patients without progression will be treated as non-progression statistically and counted in denominator toward %PFS6.

For patients who continue on treatment despite radiographic progression based upon impression of clinical benefit an/or assessment with possible pseudo-progression or a delayed response⁴⁶ (see Section 5.8), PFS will be calculated at time of first documented progression after subsequent imaging confirms progression. If subsequent imaging does not demonstrate progression, then a PFS event will not have occurred and the patient will continue with scheduled imaging assessments per protocol to determine PFS.

Re-induction and Second Course PFS (rPFS, sPFS) will be calculated in months from date of first dose of re-induction or Second Course to date of first documented radiographic and/or clinical disease progression during or after re-induction or Second Course, or death from any cause. RPFS and sPFS will be reported descriptively.

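### The ±7-day scan window that protects %PFS6 ends when treatment stops, so early stoppers without progression move to ±28 days and %PFS6 is biased modestly upward

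*Combined protocol and SAP*

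**What the plan says.** Section 7.1.2.6 (Tumor Imaging and Assessment of Disease) sets scans every 8 weeks ±7 days "during first 6 months of treatment until ascertainment of PFS6". It then gives a separate rule for patients who have stopped: "In subjects without evidence progression at treatment discontinuation, scans should be every 8 weeks", with a window of ±28 days, for up to a year of follow-up. Section 7.1.6.4 (Follow-Up Phase) repeats that rule: "Subjects who discontinue trial treatment for a reason other than disease progression will move into the Follow-Up Phase and should be assessed every 8 weeks", again ±28 days. Footnote b of the flow charts says such patients "should be assessed approximately every 8 weeks (56 ± 28 days) by radiographic imaging to monitor disease status", and footnote h restates the wider window. None of these places makes an exception for a patient still inside the first 6 months.

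Section 8.3.2, item 3, measures PFS from the first dose "to date of first documented radiographic and/or clinical disease progression or death from any cause". It adds: "The %PFS6 will be calculated as the proportion of evaluable patients progression-free at 6 months". It gives no day count for 6 months, no assessment window and no rule for a late scan.

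**The concern.** The endpoint clock runs from first dose, whereas the scan rule written to protect it runs only while the patient is on drug. A patient who stops for toxicity at, say, month 4 goes straight to the ±28-day window. A progression that a week-24 scan would have recorded as a failure may then be first documented after 6 months and scored as a success. The week-24 visit can slip past the 6-month mark. It can also come early, before the progression occurs, with the following scan due well after 6 months. Both errors raise %PFS6, and they do so in patients who could not stay on the regimen.

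**Working it through.** **Inputs from the plan.** Scans every 56 days; window ±7 days on treatment in the first 6 months, ±28 days off treatment (7.1.2.6). %PFS6 with n = 40, 20% against 40%, stated power 87% (1-sided 5%) and 78% (2-sided 5%) (8.6.2.3).

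**Assumptions, not in the plan.** Six months = 365.25/2 = 182.6 days. C1D1 is day 0 and follow-up scans are counted from it. Hazard is constant. Scan dates are uniform within the window. The patient is progression-free at week 16 (day 112).

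**Plan's own figure.** Exact one-sample binomial, n = 40: cutoff 13 gives alpha 4.3% and power 87.1%; cutoff 14 gives upper-tail alpha 1.9% and power 78.9%. The stated powers are reproduced to within a point.

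**Scan dates.** The nominal week-24 scan is day 168.
- ±7 days: days 161-175, always before day 182.6.
- ±28 days: days 140-196, up to 196 − 182.6 = 13.4 days after 6 months.

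**Chance of progression in weeks 16-24.** The daily hazard is −ln(0.20)/182.6 = 0.00881, so the chance is 1 − exp(−0.00881 × 56) = 39%. At 40% PFS6 the hazard is 0.00502 and the chance is 24%.

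**Share of those progressions not documented by 6 months, ±28 days, at 20% PFS6.**
- Scan after day 182.6: 13.4/56 = 23.9%.
- Scan before the progression: average of (t − 140)/56 over progressions at t between days 140 and 168, weighted by the exponential density = 10.5%. The next scan is due on days 196-252.
- Total: about 34%. The same calculation with ±7 days gives 0 + 2.5% = 2.5%.

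**Size.** Patients scored as successes in error = N × share stopping early while progression-free at week 16 × 0.39 × 0.34. The plan does not give that share; its only related figure is a 10% dropout allowance in 8.4.1.

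| Assumed share | Of 40 | Points of %PFS6 | Among 15 Expansion patients | Points at n = 40 |
|---|---|---|---|---|
| 5% | 2 × 0.39 × 0.34 = 0.27 | 0.7 | 0.75 × 0.39 × 0.34 = 0.10 | 0.2 |
| 10% | 4 × 0.39 × 0.34 = 0.53 | 1.3 | 1.5 × 0.39 × 0.34 = 0.20 | 0.5 |
| 15% | 6 × 0.39 × 0.34 = 0.80 | 2.0 | 2.25 × 0.39 × 0.34 = 0.30 | 0.7 |

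Subtracting the 2.5% expected under ±7 days lowers these slightly (0.25, 0.50 and 0.75 of 40). If %PFS6 is tested at cutoff 13, that net excess lifts the true one-sided error from 4.3% to about 5.4% at a 5% share and 6.6% at 10%.

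**Other anchors.** If 56 ± 28 days is counted from the last on-treatment scan (days 105-119), the next scan can be as late as day 189-203, so the problem does not depend on counting from C1D1.

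**The case against.** Several points on the other side stand.

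- **Reach.** Stages 1 and 2 (27 of 42 patients) finished enrolling in September 2017 (8.4.5), and this version is dated 10/01/2019. Their 6-month status is past, so new scan wording can affect at most the 15 Expansion patients.
- **Safeguards.** The flow charts mark imaging at the Safety Follow-Up visit, about 30 days after the last dose. Extra scans are allowed when clinically indicated, and clinical progression and death are events. These reduce the problem, but none guarantees a scan shortly before 6 months. Footnote h stresses imaging at the safety visit only after confirmed response or 24 months of treatment.
- **Endpoint status.** ORR, the primary endpoint, does not depend on this date, and 8.6.2 describes secondary analyses as descriptive. Still, %PFS6 is called key and has its own hypotheses and power in 8.6.2.3.
- **Censoring.** Section 8.3.2 also says: "Censored patients without progression will be treated as non-progression statistically and counted in denominator toward %PFS6". If that rule is applied to a patient removed early, scan timing no longer matters for that patient. It is a separate and possibly larger upward bias, and tightening the window would not remove it. The present point concerns patients who remain in follow-up and are scanned.

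A reader might infer more than the documents support. A bias of up to 6 points (6 × 0.39 = 2.3 patients of 40) would require every off-treatment scan to be late, but the window is symmetric. A scan as late as week 30 (last dose at week 18, plus 8, plus 4) needs follow-up to be counted from the last dose; the column heading can equally be read as giving only the one-year duration. A 16-week gap (8 + 4 + 4) needs a fixed calendar; read as an interval, 56 ± 28 days caps the gap at 84 days, or 12 weeks.

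**Conclusion.** The gap is real: the window that secures the 6-month status is tied to treatment, while the endpoint is tied to first dose. The resulting bias in %PFS6 is upward and modest, about 0.3-0.8 patient of 40 (roughly 1-2 points) over the whole trial and 0.1-0.3 patient (under 1 point) among the 15 Expansion patients.

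This rests on an assumed 5-15% stopping early while progression-free at week 16, uniform scan timing, constant hazard at 20% PFS6, counting from C1D1 and 6 months as about day 183. At the 40% PFS6 rate fewer progressions fall in weeks 16-24 (24% against 39%), so the bias is smaller. The safeguards above would reduce it further. Day 183 is a working convention, not the plan's definition: if 6 months meant 24 weeks (day 168), even a ±7-day scan could fall late, on day 175.

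**What to change.** 1. In 7.1.2.6, 7.1.6.4 and footnotes b and h of 6.4, state that until 6-month status has been ascertained every patient without progression, on or off treatment, is imaged every 8 weeks ±7 days counted from C1D1, and that ±28 days applies only afterwards.
2. In 8.3.2, define the PFS6 date in days and say which scan decides the status.
3. For Stage 1 and 2 patients who stopped early without progression, report the dates of the scans on either side of 6 months. Add a sensitivity analysis that counts progression first found at a late scan after 6 months as a failure.

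The cost is protocol wording, one short listing and one extra analysis. No scheduled scans are added. The downside is tighter scan scheduling for a few off-treatment patients. The scoring of censored patients needs its own correction.

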7.1.2.7 Assessment of Tumor Amenable to Percutaneous Biopsy in Expansion Cohort

Assessment of tumor likely to be safely accessible to acceptable mode of percutaneous core needle biopsy (punch, ultrasound-guided, or CT-guided) will be performed during Screening by Radiologist or qualified investigator.

7.1.3 Laboratory Procedures/Assessments

Details regarding specific laboratory procedures/assessments to be performed in this trial are provided below in Table 5.

Table 5 Laboratory Tests

Hematology	Chemistry	Urinalysis	Other
Hematocrit	Albumin	Blood	Serum β -human chorionic gonadotropin†
Hemoglobin	Alkaline phosphatase	Glucose	(β -hCG)†
Platelet count	Alanine aminotransferase (ALT)	Protein	PT (INR)
WBC (total and differential)	Aspartate aminotransferase (AST)	Specific gravity	Thyroid-stimulating hormone (TSH)
Red Blood Cell Count	Creatinine	Microscopic exam (If abnormal)	Total triiodothyronine (T3)
Absolute Neutrophil Count	Carbon Dioxide (CO ₂ or bicarbonate)	Urine pregnancy test †	Free thyroxine (T4)
Absolute Lymphocyte Count	Calcium		CA 19-9
	Chloride		Blood for correlative studies*
	Glucose		
	Phosphorus		Archival tumor sample accessioning*
	Potassium		
	Sodium		
	Magnesium		
	Total Bilirubin		
	Direct Bilirubin		
	Blood Urea Nitrogen		

† Perform urine pregnancy test on women of childbearing potential only. If urine pregnancy results cannot be confirmed as negative, a serum pregnancy test is required. *See Section 7.1.4 and Appendix 11.6 for further information on research sample collection.

Laboratory tests for screening or entry on Second Course (S) should be performed within 10 days prior to the first dose of Second Course treatment (see Section 6.3 – Second Course Pembrolizumab Flow Chart). After Second Course Cycle 1 (SC1), pre-dose laboratory procedures must be obtained within 3 days prior to dosing. Results must be reviewed by the investigator or qualified designee and found to be acceptable prior to each dose of trial treatment.

7.1.4 Tumor and Blood Sample Collection for Correlative Analyses

Tumor and blood samples will be obtained and stored from all patients for planned future correlative analyses (see Section 8.7.3), which will be performed in batch after completion of study and pending funding. In addition, for patients who consent to optional specimen banking, any left-over blood and archival tumor samples will be banked in the UCSF Tissue Core for future

research as part of the UCSF Hepatobiliary Tissue Bank, CC#124512 as a companion to this protocol. See Appendix 11.67 for correlative specimen procurement and handling instructions.

7.1.4.1 Archival Tumor Tissue Collection

In all patients, left-over diagnostic tumor block and/or slides from any tumor sampling procedure(s) (e.g. biopsy, fine needle aspiration, cytology brushings, and/or resection specimens) performed prior to enrollment, during study treatment, and/or during the Follow-Up Phase will be obtained to determine tumor PD-L1 expression status, to characterize tumor immune infiltrates/T cell subsets, and (optional) to bank for future correlative analyses as part of the UCSF Hepatobiliary Tissue Bank and Registry (CC#124512) as a companion protocol to this study. Formalin-fixed, paraffin-embedded (FFPE) tumor tissue blocks will be accessioned whenever available. In addition to blocks or if a block is not available, at least 10 unstained slides (prefer 10 μ m) plus 1 H&E slide from a tumor tissue block may be accessioned. Corresponding pathology reports from initial diagnosis and/or subsequent tumor sampling will be obtained. Specimens will be obtained from the Pathology Department for banking as soon as possible after consent and/or occurrence of post-enrollment tumor sampling and stored the Helen Diller Family Comprehensive Cancer Center (HDFCCC) Tissue Core (UCSF patients). Correlative analyses using archival tissue samples will be performed in batch at completion of study and pending funding. See Appendix 11.6 for correlative specimen procurement and handling instructions.

